#### 6.1.6.3 Study treatment dispensing

The study participants will receive sufficient study treatment to cover the period up to the next scheduled visit. Study participants are asked to return all used, partially used, and unused study treatment bottles at each visit. Should the treatment bottle dispensed at a scheduled visit be lost or damaged, a replacement bottle can be requested via the IRT system. In exceptional circumstances (e.g., pharmacist not available on the date of the scheduled visit), the investigator/delegate may contact the IRT system shortly prior to the scheduled visit (with the exception of the randomization visit [see Section 6.1.3] to obtain the treatment kit number(s) to be dispensed at the visit.

The protocol-mandated study treatment dispensing procedures may not be altered without prior written approval from the sponsor. In exceptional circumstances (e.g., if the study participant lost the study treatment between two visits, or if the study participant is unable to return to the site due to a medical emergency / hospitalization at another hospital / long travel distance), unscheduled dispensing and delivery of study treatment may occur outside of a scheduled visit. If the study treatment needs to be shipped to the study participant, the site staff must first contact the sponsor representative to check whether the dispensing and delivery process is in accordance with the sponsor/CRO's Quality System documents as well as any local or national regulatory requirements.

An accurate record of the date and amount of study treatment dispensed to each study participant must be available for inspection at any time.

Study participant will be dispensed new bottle(s) at each visit. Study drug from the newly received bottle is always to be taken in the evening at home.

The morning dose will be taken at home from the current bottle, except for Visit 5 (Week 4), Visit 7 (Week 8) and EOT visit where the morning dose will be withheld until the participant is on site and will be taken after PK laboratory samples are drawn.

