#### 7.2.5.5 Stanford Sleepiness Scale

The SSS [Hoddes 1972, Hoddes 1973] is a self-administered questionnaire that uses a 7point Likert scale, developed to quantify the subjective sleepiness at any given time. Participants will be asked to pick the response (number) that best represents how they are feeling two times during the day: once before breakfast (i.e., before the morning dose of the study treatment) and then at midday or any time before lunch to capture daytime sleepiness temporally related to intake of study treatment. Participants will be asked to answer the paper based SSS questionnaire during the first 2 weeks after randomization. This will then be transcribed by the site into the eCRF.

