7.6 Daytime sleepiness

Daytime sleepiness will be assessed using the SSS during the first two weeks of study treatment. The SSS is filled in twice daily, at breakfast before morning dose (pre-dose) and around midday, prior to lunch time (post-dose).

The SSS is a 1-item, 7-point scale that ranges between "Feeling active, vital, alert, or wide awake" and "No longer fighting sleep, sleep onset soon; having dream-like thoughts".

Daytime sleepiness is defined daily as any score > 3 on the SSS after the morning dose (post-dose).

The number of days per week with daytime sleepiness is defined as the number of diary days with at least an SSS score > 3, during the first 2 weeks of treatment only, divided by

ACT-539313		Statistical Analysis Plan
ID-082A201		for Clinical Study Report
1 April 2022, page 36/60	Confidential	Version 3
		Doc No D-22,100

the total number of diary days, times 7. A minimum of 7 diary entries during this 14-day time interval is required, otherwise the number of daytime sleepiness days will be considered missing. A diary day is a day for which the rate of daytime sleepiness is entered in the study participant's diary. This approach uses implicit imputation: if a subject does not have 14 entries but has at least 7, missing data points are given the same value as the mean of the non-missing data points of that same time point or week.

The mean number of days with daytime sleepiness pre- and post-dose during the 2-week period will be summarized by treatment group. In addition, the observed value and change from baseline at each study day will be summarized by treatment group. The number (%) of study participants with a post-dose SSS score ≤ 3 , 4, 5, 6 and 7, having a pre-dose SSS score ≤ 3 and equal to 4 will be provided by treatment group.

The SSS score pre- and post-dose over the 2-week period will be produced by treatment group using series plot (mean \pm SE) and boxplots. In addition, the series plot will be provided only for study participants with AESIs.

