11.4 Baseline

Baseline is the last non-missing assessment performed or value measured before or on the day of first dose of study treatment, unless otherwise defined in the specific analysis section.

The baseline number of BE days per week is defined as the number of diary days with at least one BE episode divided by the total number of diary days during the 14 days prior to randomization (Study day -14 to -1), times 7 [see Section 6.1.1 for definition of diary day]. A minimum of 6 entries for each of the 2 weeks preceding randomization is required per inclusion criteria to ensure study participant compliance with filling in the BE diary.

ACT-539313		Statistical Analysis Plan
ID-082A201	Confidential	for Clinical Study Report
1 April 2022, page 41/60	Confidential	Version 3
		Doc No D-22 100

Study participants with no data for a given parameter before the first treatment administration will have a missing baseline (and missing change from baseline) for this parameter.

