11.6 Missing data patterns

A monotone missing data pattern is defined as follows: given a dataset with variables Y1, Y2, ..., Yt (in that order) and Vj is missing for a particular subject, then all subsequent variables Vk, k > j, are missing for that subject. In addition, given the same dataset and Vj is observed for a particular subject, then all previous variables Vk, k < j, are also observed for that subject. Monotone missing data patterns are typically encountered when a subject prematurely withdraws from a study and is expected to be more likely seen than non-monotone missing data patterns.

In the examples below, an 'X' indicates that the variable is observed in the corresponding group and a '.' means that the variable is missing.

Subject	Y1	Y2	¥3
1	Х	Х	Х
2	Х	Х	
3	Х		

Example of monotone missing data patterns:

When missing data are non-monotone, data can also be missing at intermediate visits (i.e., missing at a given visit, but observed again at the next visit). Non-monotone missing data patterns are commonly turned into monotone missing data patterns using MI (based on MCMC), which are then subsequently analyzed using MI methods based on monotone missing data.

Example of non-monotone missing data patterns:

Subject	Y1	Y2	Y3
1	X	Х	Х
2		Х	Х
3			Х
4		Х	
5	Х		Х

11.7 Time window definitions for calculating efficacy and safety endpoints collected through diary

BE episodes (efficacy) and daytime sleepiness (safety; measured using the SSS) are the endpoints collected daily through a diary. The BE diary will be filled in from the start of the screening period until EOT while the SSS will only be filled in during the first 2 weeks of treatment (from randomization [Visit 2] to Visit 4).

Table 6 defines the time windows used to calculate number of BE episodes/days per week.

Table 6Time windows (in days) to calculate weekly averages for the efficacy
endpoints BE episodes/days collected daily through the diary

Weeks	Study day (14-day window)
1–2	1–14
3–4	15–28
5–6	29–42
7–8	43–56
9–10	57–70
11–12	71–84

For the calculation of absence of BE episodes ('Yes'/'No') during the last 4 weeks of the treatment period, a minimum of 4 out of 7 diary entries are required for days 57–63, 64–70, 71–77 and 78–84, otherwise the outcome will be set to 'No absence'. Absence of BE episodes ('Yes') is defined as BE episodes equal to 0.

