For the calculation of SSS, study days falling in the time window 2-15 will be considered for the analyses since study day 1 corresponds to assessments done on the day of the randomization where information on the SSS should not be collected.

11.8 Time window definitions for calculating exploratory efficacy and safety endpoints collected during site visits

The exploratory efficacy endpoints YBOCS-BE, PGI-S, CGI-S, PGI-C, CGI-C, EDE-Q, and HAMD-17 are collected during specific site visits [Table 7].

The safety endpoint C-SSRS[©] is collected during all site visits [Table 8].

For both efficacy and safety endpoints, if more than one assessment falls within the same time window, the assessment which is performed closest to the target study day will be considered for the analysis.

Table 7Time windows (in days) for visit-based exploratory efficacy
endpoints: YBOCS-BE, PGI-S, CGI-S, PGI-C, CGI-C, EDE-Q,
HAMD-17

Week	Target study day	Window	Endpoint
Baseline	1	1–1	YBOCS-BE, PGI-S, CGI-S, EDE-Q, HAMD-17
1	8	2-14	CGI-C, PGI-C
4	29	22-36	YBOCS-BE, PGI-S, CGI-S, PGI-C, CGI-C, EDE-Q
6	43	37–49	HAMD-17
8	57	50–64	YBOCS-BE, PGI-S, CGI-S, PGI-C, CGI-C, EDE-Q
12	85	78–92	YBOCS-BE, PGI-S, CGI-S, PGI-C, CGI-C, EDE-Q, HAMD-

CGI-C = Clinical Global Impression of Change scale; CGI-S = Clinical Global Impression of Severity scale; EDE-Q = Eating Disorder Examination Questionnaire; HAMD-17 = Hamilton Rating Scale for Depression (17-item); PGI-C = Patient Global Impression of Change scale; PGI-S = Patient Global Impression of Severity scale; YBOCS-BE = Yale-Brown Obsessive-Compulsive Scale modified for Binge Eating.

Table 8Time windows (in days) for C-SSRS©

Week	Target study day	Window	
Baseline	1	1–1	
1	8	5-11	
2	15	12–18	
4	29	22–36	
6	43	37–49	
8	57	50–64	
10	71	65–77	
12	85 78–92		

C-SSRS[©] = Columbia-Suicide Severity Rating Scale[©]

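### The planned SSS change from baseline has no value before first dose to start from, and the post-dose by pre-dose SSS table leaves out pre-dose scores of 5 to 7

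*SAP*

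**What the plan says.** - **Planned output.** SAP 7.6: "In addition, the observed value and change from baseline at each study day will be summarized by treatment group". No SSS-specific baseline is given there, so the general rule in SAP 11.4 applies: the last non-missing value before, or on the day of, first dose. The same section adds: "Study participants with no data for a given parameter before the first treatment administration will have a missing baseline". The change is then missing too.
- **When SSS is recorded.** Protocol 7.2.5.5: "Participants will be asked to answer the paper based SSS questionnaire during the first 2 weeks after randomization". SAP 11.7 agrees that "the SSS will only be filled in during the first 2 weeks of treatment (from randomization [Visit 2] to Visit 4". No screening SSS is described.
- **Which days are analysed.** SAP 11.7: "For the calculation of SSS, study days falling in the time window 2-15 will be considered for the analyses", because "study day 1 corresponds to assessments done on the day of the randomization where information on the SSS should not be collected".
- **First dose.** Protocol 6.1.6.3: "Study drug from the newly received bottle is always to be taken in the evening at home".
- **The cross-table.** SAP 7.6 tabulates post-dose scores of ≤ 3, 4, 5, 6 and 7 for participants "having a pre-dose SSS score" of ≤ 3 or equal to 4. Pre-dose here means before that morning's dose.
- **Text that disagrees.** Protocol 9.2.10 places SSS collection on Days 1–14. Protocol 7.2.5.8 lists an SSS review at Visit 2 as well as Visits 3 and 4.

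**The concern.** A change from baseline needs a value from before treatment. The SAP's collection window starts the day after the first dose, so the rule that defines baseline and the rule that selects the data appear to exclude each other.

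The morning score cannot stand in as a drug-free reference. With twice-daily dosing it comes after the previous evening's capsule. Using it to choose the rows of a table conditions on something the drug may itself have changed. Participants who are already very sleepy before breakfast (5–7) have no row.

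The subject matters because somnolence is the trial's AESI. Protocol 2.4 reports it as dose-related in the multiple-dose study (4/28, 14.3%) and absent on placebo. The SSS is the instrument chosen to follow it.

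**Working it through.** The plan states no figure to reproduce. The main check is a timeline set against the SAP's own rules; a short illustration follows.

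**1. Ratings before first dose**

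- Ratings per day: 2, before breakfast and before lunch (Protocol 7.2.5.5).
- SAP window, days 2–15: 14 days × 2 = 28 ratings.
- First dose: evening of day 1. At Visit 2 there is no earlier bottle, so the bottle dispensed that day is started that evening.
- Ratings in the window before first dose: **0 of 28**. The exact hour does not matter; any first dose on day 1 gives the same count.
- Consequence under SAP 11.4: baseline missing, change missing.
- With the protocol's Days 1–14 there are also 28 ratings, of which **at most 2**, both on day 1, could precede an evening first dose.

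**2. Is the morning score on-treatment?**

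By timing, yes: every morning in days 2–15 follows an evening dose. For a rough idea of the drug still present, Protocol 2.4 gives accumulation R of 1.6- to 2.1-fold. Assuming a one-compartment model and a 12-hour interval, the fraction remaining at the end of the interval is 1 − 1/R:

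- R = 1.6: 1 − 1/1.6 = 0.375
- R = 2.1: 1 − 1/2.1 = 0.524

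**3. How many participants might the cross-table omit?**

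The documents give no SSS distribution, so this is illustration only. Assume mean 2.2, SD 1.1, a 1-point post-dose drug effect, and a share c of that effect still present before breakfast. Counting values above 4.5 as scores 5–7, the share omitted is 1 − Φ((4.5 − 2.2 − c)/1.1):

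| c | z | Share with pre-dose 5–7 |
|---|---|---|
| 0 (also placebo) | 2.09 | 1.8% |
| 0.375 | 1.75 | 4.0% |
| 0.524 | 1.61 | 5.3% |
| 1 | 1.18 | 11.9% |

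**4. Effect on a within-day reading**

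A simulation on the same assumptions (within-day correlation 0.5, scores rounded and held to 1–7) gave these active-arm results:

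| c | Mean pre-to-post change | Pre-dose ≤ 3 and post-dose > 3 |
|---|---|---|
| 0 | 0.94 | 30.5% |
| 0.375 | 0.60 | 25.7% |
| 0.524 | 0.46 | 23.4% |
| 1 | 0.00 | 16.1% |

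The share with post-dose SSS > 3 stayed at about 39% active against 12% placebo throughout. The within-day contrast shrinks with carry-over; the between-arm comparison of post-dose scores does not.

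**The case against.** The strongest reply is that little depends on these two outputs. SAP 7.6 already plans, by arm and without restriction on the pre-dose score, the mean number of sleepiness days pre- and post-dose, observed values by study day, and series plots and boxplots of both scores. Morning carry-over would appear there as a difference between arms. The endpoint itself, post-dose SSS > 3, is an absolute cut-off that needs no baseline. Somnolence is also asked about at each visit and tabulated as an AESI. All of this stands. A reader might infer that the plan hides sedation; the documents do not support that.

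A second reply is that a complete absence of baseline values is too absolute. SAP 11.3 distinguishes treatment day from study day, so a first dose on day 2 is possible and would leave a usable rating inside the window. Protocol 9.2.10 and 7.2.5.8 suggest that some day 1 entries may exist. Protocol 9.2.10 also defines the score as following the morning dose, which sits awkwardly with an evening first dose on day 1. This stands too, but it argues for reconciling the passages. As written, the SAP window discards any day 1 entry, and SAP section 12 does not record the move from Days 1–14 to days 2–15 as a change.

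Finally, baseline might have been meant as the same-day pre-dose score. The SAP does not say so, and that score is on-treatment.

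**Conclusion.** The concern holds, confined to two descriptive safety outputs. The SSS change from baseline is void as written: 0 of 28 ratings precede a first dose taken on day 1, with exceptions only where the first dose slipped. This rests on the documents' rules and on reading Protocol 6.1.6.3 as placing the first dose on the day of randomization.

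The cross-table conditions on an on-treatment score and omits pre-dose 5–7. It can therefore lose sleepier active-arm participants selectively. Under the assumed distribution the omission is about 4% to 5% of the active arm against about 2% on placebo, and 12% with full carry-over; none of these shares comes from the documents.

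The main daytime-sleepiness count, the by-arm pre- and post-dose summaries and plots, and the AESI tables are unaffected.

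**What to change.** In SAP 7.6:

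1. Delete the SSS change from baseline, or define baseline only as a day 1 SSS recorded before first dose, for participants who have one, and report how many that is.
2. Show post-dose SSS for every pre-dose category, including 5, 6 and 7, with an all-participants row by arm.
3. Label pre-dose SSS as an on-treatment outcome, so that it is read between arms and not as a drug-free reference.

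Reconcile the days 2–15 window in SAP 11.7 with Protocol 9.2.10 and 7.2.5.8, and record the outcome in SAP section 12. If baseline is to come from day 1 entries, the window must admit them for that purpose.

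The cost is SAP wording and table shells. Adding a new rating at Visit 2 is not proposed: it would change data collection, and this SAP version is dated 1 April 2022, when participants had already been dosed and 9 had already stopped through site closure. It could not supply a baseline for them.

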7.7 Withdrawal symptoms

7.7.1 Benzodiazepine Withdrawal Symptoms Questionnaire

The BWSQ consists of 20 items with each item rated by the subject as either 0 (No), 1 (Yes-moderate), or 2 (Yes-severe). The change in BWSQ Total score (possible range: 0 to 40) from the last available assessment during the treatment period to EOS will be summarized. Observed values will also be summarized.

The number (%) of study participants with a BWSQ Total score above 20 will be tabulated by visit (EOT and EOS).

The number (%) of study participants with one or more BWSQ symptom scored as 'severe' will be tabulated by visit (EOT and EOS).

In addition, withdrawal symptoms after study treatment discontinuation will be assessed through the incidence of AEs occurring during the safety follow-up period. As described in the respective section [Section 7.2], the incidence of AEs occurring during the safety follow-up period will be summarized.

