- 8. All participants will be asked to return for an EOT visit. For participants who prematurely discontinue study treatment, the EOT visit will occur within 5 days of the last intake of study treatment. For participants who complete the treatment period as planned, the Week 12 visit corresponds to the EOT visit.
- 9. During unscheduled visits, additional assessments may be performed at the discretion of the investigator. The assessments in brackets are recommended to be performed on an unscheduled visit, based on medical judgment.

10. Stanford Sleepiness Scale to be filled in for the first 2 weeks of study treatment, twice daily, at breakfast (before morning dose) and around midday, prior to lunch time.

AE = adverse event; BP = blood pressure; BWSQ = Benzodiazepine Withdrawal Symptom Questionnaire; CGI-C = Clinical Global Impression of Change scale; CGI-S = Clinical Global Impression of Severity scale; C-SSRS© = Columbia Suicide Severity Rating Scale©; eCRF = electronic Case Report Form; ECG = electrocardiogram; EDE-Q: Eating Disorder Examination Questionnaire; EOS = End-of-Study; EOT = End-of-Treatment; HAMD-17 = Hamilton Rating Scale for Depression (17-item); ICF = informed consent form; IMP = Investigational Medicinal Product; IRT = Interactive Response Technology; MINI© = Mini International Neuropsychiatric Interview©; NA = not applicable; PGI-C = Patient Global Impression of Change scale ; PGI-S = Patient Global Impression of Severity scale; PK = pharmacokinetic(s); PR = pulse rate; RR = respiratory rate; SAE = serious adverse event; SCID-5 = Structured Clinical Interview for DSM-5; To = temperature; U1 = unscheduled visit; V = visit; WOCBP = women of childbearing potential; YBOCS-BE = Yale-Brown Obsessive-Compulsive Scale Modified for Binge Eating.

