#### 5.9.1 Study treatment premature discontinuation

The decision to prematurely discontinue study treatment may be made by the study participant, the investigator/delegate, or the sponsor personnel.

The investigator/delegate has the option of prematurely discontinuing study treatment for a given study participant in response to an AE, a diagnostic or therapeutic procedure, a laboratory abnormality, or for administrative reasons. If study treatment is interrupted by the study participant for any reason, she/he must inform the investigator/delegate as soon as possible. Study treatment dose interruptions must be recorded in the eCRF.

The investigator/delegate must permanently discontinue study treatment for a given study participant if, on balance, he/she believes that continued administration would be contrary to the best interests of the study participant.

Study-specific criteria for permanent discontinuation of study treatment are described in Sections 5.9.1.1 to 5.9.1.4.

The main reason for permanent discontinuation of study treatment (e.g., due to pre-specified study treatment discontinuation criteria, an AE, lack of efficacy, study termination) must be documented in the eCRF.

A study participant who prematurely discontinues study treatment is not considered as withdrawn from the study.

The study participant who prematurely discontinues study treatment or who is permanently discontinued from study treatment will be asked to return for an EOT visit within 1 to 5 days of last intake of study treatment and thereafter to attend follow-up visits as defined in the schedule of activities [Table 1, Section 7.2].

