#### 7.2.5.6 Benzodiazepine Withdrawal Symptom Questionnaire

The BWSQ assesses the occurrence of symptoms which might be experienced by study participants after discontinuation of treatment with ACT-539313 [Tyrer 1990]. The questionnaire consists of 20 items. The symptoms will be rated from 0 (No), 1 (Yes-moderate) to 2 (Yes-severe). The questionnaire will be self-administered using the touchscreen device at EOT visit and EOS visit.

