2 STUDY DESIGN AND FLOW

[figure not shown]
This is a Phase 2, multicenter, double-blind, randomized, placebo-controlled, parallel-group, proof-of-concept study assessing ACT-539313 at a dosing regimen of 100 mg b.i.d. vs placebo over a 12-week treatment period in adult participants (18 to 55 years of age) with moderate to severe binge eating disorder (BED).

Approximately 120 participants will be randomized to either ACT-539313 at a dose of 100 mg b.i.d., or placebo in a 1:1 ratio.

The study will be conducted at approximately 30 sites in the USA.

The study design is shown in Figure 1.

Figure 1Study design for ID-082A201

b.i.d. = twice daily; EOS = End-of-Study; EOT = End-of-Treatment; V = Visit.

The study comprises the following 3 periods: the screening period, the treatment period and the safety follow-up period.

The **screening period** starts with the signing of the ICF at Visit 1 and ends with Randomization at Visit 2 or with a screening failure. It lasts a minimum of 14 days and up to 28 days.

The **treatment period** starts with the administration of the first dose of study treatment and ends on the day of the last dose of study treatment. The study participants will be treated for 12 weeks.

The **safety follow-up period** starts on the day after the last dose of study treatment and ends at the EOS visit (10 ± 3 days after EOT).

See Section 11.2 for detailed definitions of the study periods.

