11.2 Study periods

The Screening period is defined as the time from the informed consent date until one day before the study treatment start date, or date of screening failure.

The treatment period is defined as the time from the day of study treatment start until the day of EOT (Week 12), or, for those who prematurely discontinued study treatment (i.e., those without an EOT date), until the day of study treatment end date. In case of missing

ACT-539313		Statistical Analysis Plan
ID-082A201	Confidential	for Clinical Study Report
1 April 2022, page 40/60	Confidential	Version 3
		Doc No D-22.100

study treatment end date, EOT will be imputed using the last available visit/assessment date.

The safety follow-up period is defined as the time from one day after EOT until EOS date.

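### The BWSQ and HAMD-17 withdrawal change starts from the last assessment in the treatment period, which for premature discontinuers ends before their EOT-visit form is completed

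*SAP*

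**What the plan says.** SAP 7.7.1 plans a summary of "The change in BWSQ Total score (possible range: 0 to 40) from the last available assessment during the treatment period to EOS". SAP 7.7.2 uses the same starting point for the HAMD-17 total score.

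SAP 11.2 defines the treatment period. For completers it runs to the day of the Week 12 EOT visit. The rule differs "for those who prematurely discontinued study treatment (i.e., those without an EOT date), until the day of study treatment end date". SAP 11.1 sets the treatment end date as the latest recorded dose intake.

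The protocol fixes when the forms are completed:
- BWSQ (Protocol 7.2.5.6): "The questionnaire will be self-administered using the touchscreen device at EOT visit and EOS visit".
- Premature discontinuers (Protocol 5.9.1) "will be asked to return for an EOT visit within 1 to 5 days of last intake of study treatment". Table 1 gives the same window, and its footnote 8 says "All participants will be asked to return for an EOT visit".
- Completers are still dosing at the EOT visit. Protocol 6.1.6.3 says that at that visit "the morning dose will be withheld until the participant is on site and will be taken after PK laboratory samples are drawn".

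Protocol Table 2 and Protocol 9.2.10 define the endpoint as the change from Week 12/EOT to EOS in BWSQ and HAMD-17. SAP 12 lists no change or clarification on this point, and SAP 11.8 gives the BWSQ no visit window.

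**The concern.** Withdrawal on stopping treatment is a named safety endpoint, and the protocol's definition covers participants who stop early. The SAP replaces the protocol's starting visit with a starting period. For early stoppers, that period closes before the only BWSQ form that could serve as the start. A stated rule therefore departs from the protocol endpoint, and the SAP does not list it as a change.

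For the BWSQ, discontinuers drop out of the change row. For HAMD-17, the change can start weeks before the last dose, so improvement on treatment and worsening after stopping are added together and can cancel.

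SAP 11.2 also describes premature discontinuers as lacking an EOT date, although the protocol asks all of them to attend an EOT visit. A programmer could therefore take those who attend to have a treatment period that lasts until that visit. That gives a different number, and the SAP does not say which is meant.

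**Working it through.** **Figures in the plan.** The BWSQ has 20 items scored 0 to 2, so the maximum is 20 × 2 = 40, as SAP 7.7.1 states. The longest participation is 28 (screening) + 87 (Day 85 + 2) + 13 (EOS) = 128 days, as Protocol 4.1.1 states. This confirms that EOS is counted from the EOT visit.

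**Days since last dose (last dose = day 0).** Inputs: the EOT window for premature stops (Protocol 5.9.1 and Table 1), EOS at 10 ± 3 days after EOT (Table 1), and the treatment period (SAP 11.1 and 11.2).

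| | Completer | Premature discontinuer |
|---|---|---|
| Treatment period ends | day of Week 12 EOT visit | day 0 |
| EOT-visit form | about day 0 | day 1 to 5 |
| EOS form | day 7 to 13 | 1 + 7 = 8 to 5 + 13 = 18 |
| BWSQ forms inside the period | 1 | 0 |

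**BWSQ.** No form lies in the period, so the change is missing for every discontinuer seen in the scheduled window. SAP 14.4 and 14.5 count 9 participants who discontinued through site closure: 9/120 = 7.5% of the planned number. At most 120 − 9 = 111 could then contribute. If 20% stopped early, the figures would be 24 missing and at most 96 contributing. That 20% is an assumption, borrowed from the allowance for missing Week 11–12 data in Protocol 9.4.

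**HAMD-17.** On treatment it is scored at Week 6 (Day 43 ± 2, so Day 41 to 45) and at the EOT visit. With the EOT-visit score outside the period, the start falls back to Week 6:
- Stop on Day 60: EOS is Day 68 to 78. The interval is 68 − 45 = 23 to 78 − 41 = 37 days.
- Stop on Day 80: EOS is Day 88 to 98. The interval is 88 − 45 = 43 to 98 − 41 = 57 days, of which 80 − 45 = 35 to 80 − 41 = 39 days are on treatment.

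Completers' intervals are 7 to 13 days. As an illustration with assumed values, a 2-point improvement between Week 6 and the last dose, followed by a 2-point rise on stopping, gives −2 + 2 = 0.

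**The other reading of SAP 11.2.** If attending the EOT visit extends the period to that visit, the change can be computed. It then runs from 1–5 to 8–18 days off drug, against about 0 to 7–13 for completers. How much drug remains can be illustrated from the accumulation of 1.6 to 2.1 in Protocol 2.4. Assuming one compartment and 12-hour dosing, R = 1/(1 − 2^(−12/t½)) gives a half-life of 8.5 to 12.9 hours. About 14% to 27% then remains after 1 day and 0.2% or less after 5 days, so the starting form could already contain withdrawal symptoms. The two readings are alternatives, and their effects do not add.

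**The case against.** The strongest reply is that little is lost. SAP 7.7.1 also plans BWSQ observed values, the count with a total above 20 and the count with any severe item, the last two by visit at EOT and EOS. These do not depend on the treatment period, so discontinuers' forms are reported. Only the completers' change starts on drug, and for the BWSQ that is essentially what the SAP rule leaves. The 1-to-5-day gap comes from the protocol's visit window, and no SAP wording can create an on-drug form. All of this stands and limits the point to the change summaries. It does not explain why the SAP departs from the protocol endpoint without saying so, and it does not cover HAMD-17.

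A reader might infer more than the documents support:
- **Early off-drug AEs are left out of follow-up.** SAP 11.2 says "The safety follow-up period is defined as the time from one day after EOT until EOS date", while SAP 2 says that follow-up "starts on the day after the last dose of study treatment and ends at the EOS visit". These conflict only if EOT means the visit. Protocol 7.1 uses EOT for the day of the last dose, and with that meaning they agree. The TEAE tables run to EOS in any case.
- **HAMD-17 falls back to Day 1 for stops before Week 6.** The Day 1 score is the baseline (SAP 11.4 and Table 7). Newly dispensed drug is first taken that evening (Protocol 6.1.6.3), so the score is pre-dose. Whether it counts as within the treatment period is doubtful; only the Week 6 fallback is clear.
- **A definite bias in the mean BWSQ change.** The documents give no size for a symptom rise, and the summaries are by arm, one of which is placebo.
- **A 20% discontinuation rate.** Protocol 9.4 allows for missing Week 11–12 data, which can also arise from too few diary entries.

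The protocol window is also given as within 5 days (Table 1 footnote 8 and Protocol 7.1), so a same-day EOT form is conceivable. The 1-to-5-day schedule does not provide for one.

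**Conclusion.** The point holds for the BWSQ and HAMD-17 change summaries. For premature discontinuers seen in the scheduled window, SAP 7.7.1 with 11.1 and 11.2 gives no BWSQ change. SAP 7.7.2 gives a HAMD-17 change that starts at Week 6 where one exists. Neither is the protocol's Week 12/EOT-to-EOS endpoint.

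The size that the documents support is at least the 9 site-closure participants, 7.5% of 120, provided that they were dosed and attended both EOT and EOS. Any who missed a visit would have no change under any rule. Completers are handled correctly. These are untested descriptive safety summaries, and the primary analysis is untouched. The correction is still worth making, because it restores a named safety endpoint by wording alone.

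**What to change.** - **SAP 7.7.1 and 7.7.2:** define the start of the change as the EOT-visit assessment, whether Week 12 or premature, with no fallback to an earlier HAMD-17 visit.
- **Tables:** show the change separately for participants who completed 12 weeks and for premature discontinuers. For the latter, add days since last dose at EOT and EOS. Read the completers as the main description of withdrawal.
- **SAP 11.2:** delete the parenthesis that equates premature discontinuers with participants who have no EOT date. State that follow-up starts the day after the last dose, as in SAP 2. The follow-up wording is only a clarification.

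The cost is SAP wording and one split of existing tables; no new data are needed. The discontinuer group will be small, its starting value stays 1 to 5 days off drug, and its results can only be descriptive.
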